Attachment 6: Anticipated Events

An anticipated event is an AE (serious or non-serious) that commonly occurs as a consequence of the underlying disease or condition under investigation (disease-related) or background regimen.

For the purposes of this study the following events will be considered anticipated events:

1. Severe hypoglycemia. This is defined as a BG reading of <70 mg/dL and/or clinical signs and symptoms consistent with hypoglycemia even in the absence of a BG reading.
2. Diabetic Ketoacidosis (DKA). This is a condition of ketosis and metabolic acidosis that can occur in individuals with T1D.

Both severe hypoglycemia and DKA may present along a spectrum of severity. The site principal investigator will be responsible for the AE classification according to the definitions in Section 12.

Reporting of Anticipated Events

These events will be captured on the CRF and in the database and will be reported to the sponsor as described in Section 12.4.1, All Adverse Events. Any event that meets SAE criteria will be reported to the sponsor within the appropriate timeline as described in Section 12.4.2, Serious Adverse Events. These anticipated events are exempt from expedited reporting as individual single cases to health authorities. However, if based on an aggregate review, it is determined that an anticipated event is possibly related to study agent, the sponsor will report these events in an expedited manner.

Anticipated Event Review Committee (ARC)

An Anticipated Event Review Committee (ARC) will be established to perform reviews of pre-specified anticipated events at an aggregate level. The ARC is a safety committee within the sponsor's organization that is independent of the sponsor's study team. The ARC will meet to aid in the recommendation to the sponsor's study team as to whether there is a reasonable possibility that an anticipated event is related to the study agent. As this is a blinded study, an unblinded physician within the sponsor's organization not involved with the study but with subject matter expertise will be available to assist the ARC in the assessment and categorization of AEs if needed.

Statistical Analysis

Details of statistical analysis of anticipated events, including the frequency of review and threshold to trigger an aggregate analysis of anticipated events will be described in a separate Anticipated Events Safety Monitoring Plan (ASMP).

INVESTIGATOR AGREEMENT

THIS APPENDIX APPLIES TO ALL CURRENT APPROVED VERSIONS OF PROTOCOL CNTO148DML2001

GCP Compliance: This study will be conducted in compliance with Good Clinical Practice, and applicable regulatory requirements.

Confidentiality Statement

The information provided herein contains Company trade secrets, commercial or financial information that the Company customarily holds close and treats as confidential. The information is being provided under the assurance that the recipient will maintain the confidentiality of the information under applicable statutes, regulations, rules, protective orders or otherwise.

COVID-19 APPENDIX

GUIDANCE ON STUDY CONDUCT DURING THE COVID-19 PANDEMIC

It is recognized that the Coronavirus Disease 2019 (COVID-19) pandemic may have an impact on the conduct of this clinical study due to, for example, self-isolation/quarantine by participants and study-site personnel; travel restrictions/limited access to public places, including hospitals; study site personnel being reassigned to critical tasks.

In alignment with recent health authority guidance, the sponsor is providing options for study -related participant management in the event of disruption to the conduct of the study. This guidance does not supersede any local or government guidelines or requirements or the clinical judgement of the investigator to protect the health and well-being of participants and site staff. If at any time a participant's safety is considered to be at unacceptable risk, study intervention will be discontinued, and study follow-up will be conducted.

Scheduled visits that cannot be conducted in person at the study site will be performed to the extent possible remotely/virtually or delayed until such time that on-site visits can be resumed. At each contact, participants will be interviewed to collect safety data. Key efficacy endpoint assessments should be performed if required and as feasible. Participants will also be questioned regarding general health status to fulfill any physical examination requirement.

Every effort should be made to adhere to protocol-specified assessments for participants on study intervention, including follow up. Modifications to protocol-required assessments may be permitted after consultation between the participant and investigator, and with the agreement of the sponsor (see below).

The sponsor will continue to monitor the conduct and progress of the clinical study, and any changes will be communicated to the sites and to the health authorities according to local guidance.

If a participant has tested positive for COVID-19, the investigator should contact the sponsor's medical officer or designee to discuss plans for study intervention and follow-up.

ADDITIONAL ELEMENTS, WHERE APPLICABLE:

- Certain protocol-mandated visits to the study site may not be possible during the COVID-19 outbreak. Therefore, temporary measures may be implemented if considered appropriate by the sponsor and investigator to maintain continuity of participant care and study integrity. Certain measures, such as those listed below, may be necessary and should be instituted in accordance with applicable (including local) laws, regulations, guidelines, and procedures:
 - remote (e.g. by phone / telemedicine) or in-person, off-site (eg, in-home) interactions between site staff (or designees) and participants for study procedures e.g. those related to safety monitoring / efficacy evaluation / study intervention storage and administration (including training where pertinent)

- procurement of study intervention by participants (or designee) or shipment of study intervention from the study site directly to participants for at home administration (including the potential for self-administration of study intervention)
- laboratory assessments using a suitably accredited local laboratory; for selected measures (eg, urine pregnancy), home testing may be employed
- other procedures, eg, imaging, may be conducted at an appropriate facility
- Missed assessments/visits will be captured in the clinical trial management system for protocol deviations. Discontinuations of study interventions and withdrawal from the study should be documented with the prefix “COVID-19-related” in the case report form (CRF).
 - other relevant study data elements impacted by the pandemic should also be documented / labeled as “COVID-19-related” in CRFs and / or other study systems, as directed by detailed sponsor guidance. These may include missed / delayed / modified study visits / assessments / dosing, and instances where temporary measures such as those above are implemented.
- The sponsor will evaluate the totality of impact of COVID-19 on collection of key study data and additional data analyses will be outlined in study SAP(s).
- Exclusion: a potential participant with the following features will be excluded from participating in the study protocol:
 - During the 6 weeks prior to baseline, have had ANY of (a) confirmed SARS-CoV-2 (COVID-19) infection (test positive), OR (b) suspected SARS-CoV-2 infection (clinical features without documented test results), OR (c) close contact with a person with known or suspected SARS-CoV-2 infection
 - Exception: may be included with a documented negative result for a validated SARS-CoV-2 test
 - (i) obtained at least 2 weeks after conditions (a), (b), (c) above (timed from resolution of key clinical features if present, e.g. fever, cough, dyspnea)

AND
 - (ii) with absence of ALL conditions (a), (b), (c) above during the period between the negative test result and the baseline study visit

- NOTES on COVID-related exclusion:
 1. If a participant is excluded due to recent COVID-19-related features, the reason for screen failure should be documented in the case report form under the exclusion criterion of having a condition for which participation would not be in the participant's interest or could confound study assessments.
 2. The field of COVID-related testing (for presence of, and immunity to, the SARS-CoV-2 virus) is rapidly evolving. Additional testing may be performed as part of screening and/or during the study if deemed necessary by the investigator and in accordance with current regulations / guidance from authorities / standards of care.
- Precaution: for those who may carry a higher risk for severe COVID-19 illness (e.g. those aged over 65 years), follow guidance from local health authorities when weighing the potential benefits and risks of enrolling in the study, and during participation in the study.

INVESTIGATOR AGREEMENT

I have read this protocol and agree that it contains all necessary details for carrying out this study. I will conduct the study as outlined herein and will complete the study within the time designated.

I will provide copies of the protocol and all pertinent information to all individuals responsible to me who assist in the conduct of this study. I will discuss this material with them to ensure that they are fully informed regarding the study intervention, the conduct of the study, and the obligations of confidentiality.

Coordinating Investigator (where required):

Name (typed or printed): _____

Institution and Address: _____

Signature: _____ Date: _____

(Day Month Year)

Principal (Site) Investigator:

5.5. Other Efficacy Variables.....	23
5.6. Exploratory Efficacy Variables	23
6. SAFETY	24
6.1. Adverse Events	24
6.2. Clinical Laboratory Tests.....	25
6.3. Vital Signs	25
7. CLINICAL PHARMACOLOGY	25
7.1. Pharmacokinetics.....	25

7.2.	Immunogenicity	27
7.3.	Pharmacodynamic	27
7.4.	Pharmacokinetic/Pharmacodynamic Relationship.....	28
REFERENCES.....		28
ATTACHMENTS.....		28

ABBREVIATIONS

ADA	American Diabetes Association
ADR	adverse drug reaction
AE	adverse event
ALT	alanine aminotransferase
ANCOVA	analysis of covariance
anti-HBc	hepatitis B core antibody
ARC	Anticipated Event Review Committee
AS	ankylosing spondylitis
AST	aspartate aminotransferase
AUC	area under the concentration-time curve
BCG	Bacille Calmette-Guérin
BG	blood glucose
BSA	body surface area
CD	Crohn's Disease
CDC	Centers for Disease Control and Prevention
CDE	certified diabetes educator
CL/F	apparent total systemic clearance
CMV	cytomegalovirus
CRF	case report form(s) (paper or electronic as appropriate for this study)
DBL	data base locks
DKA	diabetic ketoacidosis
DMC	Data Monitoring Committee
EBV	Epstein-Barr virus
eDC	electronic data capture
eDiary	electronic diary
FDA	Food and Drug Administration
GAD-65	Glutamic acid decarboxylase
GCP	Good Clinical Practice
HbA1c	hemoglobin A1c
HBsAg	hepatitis B surface antigen
HBV	hepatitis B virus
HCV	hepatitis C virus
HIV	human immunodeficiency virus
HLA	Human leukocyte antigen
HPV	human papillomavirus
IAC	Interim Analysis Committee
IB	Investigator Brochure
ICF	informed consent form
ICH	International Conference on Harmonisation
IEC	Independent Ethics Committee
IFU	instructions for use
IL	interleukin-
IND	Investigational New Drug
IRB	Institutional Review Board
IWRS	interactive web response system
LQC	lowest quantifiable concentration
MedDRA	Medical Dictionary for Regulatory Activities
MHC	major histocompatibility complex
mITT	modified intent-to-treat
MMRM	mixed model for repeated measures
MMTT	Mixed-meal Tolerance Test
MS	multiple sclerosis
MTX	methotrexate
NAb	neutralizing antibody
NONMEM	NONlinear Mixed Effects Modeling

NPH	Neutral Protamine Hagedorn
PBMC	peripheral blood mononuclear cell
PD	pharmacodynamic(s)
PE	physical examination
PFS-U	UltraSafe Passive® Delivery System assembled with PFS
pJIA	polyarticular juvenile idiopathic arthritis
PK	pharmacokinetic(s)
PQC	Product Quality Complaint
PsA	psoriatic arthritis
PsO	psoriasis
q2w	every 2 weeks
q4w	every 4 weeks
RA	rheumatoid arthritis
SAE	serious adverse event
SAP	Statistical Analysis Plan
SC	subcutaneous
SD	standard deviation
SIPPM	Study Site Investigational Product and Procedures Manual
SLE	systemic lupus erythematosus
SUSAR	suspected unexpected serious adverse reaction
T1D	type 1 diabetes
TB	tuberculosis
TE	target engagement
TNF α	tumor necrosis factor alpha
UC	ulcerative colitis
ULN	upper limit of normal
V/F	apparent volume of distribution

1. INTRODUCTION

This statistical analysis plan (SAP) contains definitions of analysis sets, derived variables, and statistical methods for the analysis of efficacy, safety, pharmacokinetics, and immunogenicity of golimumab in the CNTO148DML2001 study. This SAP is specific to the Week 52 database lock (DBL).

1.1. Trial Objectives

Primary Objectives

The primary objective is to determine if golimumab can preserve β -cell function in children and young adults with newly diagnosed T1D.

Secondary Objectives

- To evaluate the impact of golimumab on measures of diabetes control in this subject population.
- To evaluate the off-therapy durability of golimumab on measures of diabetes control in this subject population.
- To determine the safety and tolerability of golimumab in children and young adults with T1D.
- To evaluate the pharmacokinetics (PK) and immunogenicity of golimumab in this specific subject population with T1D.

[figure not shown]
Exploratory Objectives

Exploratory objective is to evaluate how golimumab impacts immunologic profiles and indicators of β -cell stress, and the correlation with efficacy and safety endpoints in this study.

1.2. Trial Design

This is a Phase 2a randomized, double-blind, placebo-controlled, parallel-group, multicenter, study of golimumab in children and young adults with new onset T1D. Confirmation of the autoimmune nature of T1D in subjects will be determined by positivity of at least one T1D-associated autoantibody. Subjects must also show evidence of residual endogenous β -cell function, defined by a C-peptide level of ≥ 0.2 pmol/mL from a 4-hour MMTT at study screening, and be able to be randomized within 28 days of screening and 100 days of diagnosis.

A diagram of the study design is provided below and as depicted in **Error! Reference source not found.**, approximately 81 subjects will be randomly assigned in a 2:1 ratio to receive golimumab or matching placebo therapy and be stratified based on a C-peptide AUC of < 0.66 pmol/mL or ≥ 0.66 pmol/mL from a 4-hour MMTT conducted at study screening. Following screening, subjects must be randomized within 28 days. Following randomization there will be a 52-week treatment period with study agent followed by a 52-week off-therapy follow-up period. Two planned database locks (DBLs) will occur, at Week 52 and at Week 104.

Figure 1: Schematic Overview of the Study

Efficacy assessments will be performed according to the Schedules of Activities. Serum samples for PK, immunogenicity, and exploratory assessments will be collected at the timepoints shown in the Time and Events Schedule in the protocol.

An independent Data Monitoring Committee (DMC) will be commissioned to continually assess the safety of study subjects. The DMC will evaluate an interim analysis based on 4-hour C-peptide AUC in response to an MMTT after at least 60% of subjects complete their Week 26 MMTT assessment. The primary goal of this interim analysis is to obtain an early read on treatment effect to facilitate planning of future studies.

1.3. Statistical Hypotheses for Trial Objectives

The primary hypothesis to be tested in this study is that golimumab is superior to placebo in maintaining β -cell function in children and young adults with newly diagnosed T1D as measured by MMTT-stimulated 4-hour C-peptide AUC at Week 52.

1.4. Sample Size Justification

This study is designed to enroll approximately 81 subjects in order to have sufficient power to detect a difference between the golimumab groups and the placebo group for the primary efficacy endpoint. The rationale for the study sample size is based on the hypothesis tests for the primary efficacy endpoint.

The sample size calculation is based on the primary endpoint, an MMTT 4-hour C-peptide AUC at Week 52. Due to skewed C-peptide AUC data, normalizing transformation of $\log(AUC + 1)$ is

applied for sample size assessment. The method has been well accepted and used in numerous clinical studies. Based on published data, a common standard deviation (SD) of log (AUC+1) of 0.215 is assumed, and the back-transformed means for 4-hour C-peptide AUC are assumed to be 0.385 and 0.635 for the placebo and golimumab groups respectively, ie the expected treatment difference (back-transformed) is 0.25. Based on these assumptions, with 81 subjects (54 on golimumab and 27 on placebo), there is 90% power to detect a treatment difference with a 2-sided significance level of 0.05 through a 2-sample t-test.

1.5. Randomization and Blinding

1.5.1 Randomization

Central randomization will be implemented in this study. Approximately 81 subjects who meet all enrollment criteria and have all Day 1 procedures performed will be randomly assigned to 1 of 2 treatment groups based on a computer-generated randomization schedule prepared before the study by, or under the supervision of, the sponsor. The randomization will be balanced by using randomly permuted blocks and will be stratified on subject baseline C-peptide AUC (<0.66 pmol/mL, ≥0.66 pmol/mL) derived from the 4-hour MMTT conducted at screening. The interactive web response system (IWRS) will assign a unique treatment code, which will dictate the treatment assignment and matching study agent kit for the subject. Members of the study site will have unique user and personal identification numbers to contact the IWRS and must provide relevant subject details to uniquely identify the subject.

1.5.1. Blinding

This will be a randomized, double-blind, placebo-controlled study. To maintain the study blind, the study agent container will have a multipart label containing the study name, study agent number, reference number, and other information on each part. The label will not identify the study agent in the container. However, if it is necessary for a subject's safety, the study blind may be broken and the identity of the study agent ascertained. The study agent number will be entered in the case report form (CRF) when the study agent is administered. The study agents will be identical in appearance and will be packaged in identical containers.

The investigator will not be provided with randomization codes. The codes will be maintained within IWRS, which has the functionality to allow the investigator to break the blind for an individual subject.

Data that may potentially unblind the treatment assignment will be handled with special care to ensure that the integrity of the blind is maintained and the potential for bias is minimized. This can include making special provisions, such as segregating the data in question from view by the investigators, clinical team, or others as appropriate until the time of database lock and unblinding.

Under normal circumstances, the blind should not be broken until all subjects have completed the study and the database is finalized. Otherwise, the blind should be broken only if specific

emergency treatment/course of action would be dictated by knowing the treatment status of the subject. In such cases, the investigator may in an emergency determine the identity of the treatment by contacting the IWRS. It is recommended that the investigator contact the sponsor or its designee if possible to discuss the particular situation before breaking the blind. Telephone contact with the sponsor or its designee will be available 24 hours per day, 7 days per week. In the event the blind is broken, the sponsor must be informed as soon as possible. The date, time, and reason for the unblinding must be documented by the IWRS in the appropriate section of the electronic case report form (eCRF), and in the source document.

The documentation received from the IWRS indicating the code break must be retained with the subject's source documents in a secure manner so as to not unblind the treatment assignment to the subject, the study site, or sponsor personnel. The investigator is also advised not to reveal the study treatment assignment to the subject, the study site, or sponsor personnel.

Subjects who have had their intervention assignment unblinded by the investigator will not be eligible to receive further study intervention, but should continue to complete scheduled evaluations.

An independent DMC will monitor the safety of the study in an unblinded subject-level fashion on a regular basis and whenever deemed necessary. In addition, the Sponsor Medical Monitor will review safety data in a blinded manner as the study is ongoing.

2. GENERAL ANALYSIS DEFINITIONS

2.1. Visit Windows

Nominal visits will be used for all by visit analyses.

2.2. Analysis Sets

2.2.1. Efficacy Analysis Set(s)

Unless otherwise specified, all analyses will use the full analysis set, which is defined below.

- **The full analysis set** includes all randomized subjects who take at least one dose (complete or partial) of study agent.
- **The per-protocol (PP) analysis set** will consist of the full analysis set who complete 52 weeks of treatment (as described above) and have no major protocol deviations that may affect the interpretation of the primary efficacy endpoint.
- **The extended efficacy analysis set** includes all randomized subjects in this study and an additional 45 placebo subjects from three external trials. The three Immune Tolerance Network (ITN) funded trials had similar eligibility criteria and trial set-up.^{1,2,3} To match population in the study, only those aged between 6 and 21 will be included in the analysis.

Efficacy data will be analyzed according to the randomization assignment regardless of the actual treatment received.

2.2.2. Safety Analysis Set

The safety analysis set includes all randomized subjects who received at least 1 (partial or complete) dose of study agent, i.e., the treated population. In this study, the safety analysis set is the same as the full analysis set.

In the safety analyses, subjects will be analyzed according to the treatment they actually received, regardless of the treatments they are randomized to. More details are provided in Section 6.

2.2.3. Pharmacokinetics Analysis Set

The pharmacokinetics evaluable (PKE) analysis set includes treated subjects (who received at least 1 injection) who have sufficient PK samples for analysis.

Pharmacokinetics analyses will be performed using the PKE analysis set.

2.3. Baseline Measurements

The baseline measurement of a parameter is defined as the closest measurement taken prior to or on the same day as the Week 0 administration except otherwise specified.

2.4. Definition of Subgroups

To evaluate the consistency in the key efficacy over demographics, baseline characteristics, prior and baseline medication use, subgroup analyses will be performed when sample sizes are permitted (at least 5 subjects for each treatment group within a subset). The subgroups include, but are not limited to, the following:

Baseline demographics:

- Sex (male, female)
- Baseline Age (<12, 12-18, ≥18)
- Baseline weight (<45kg, ≥45kg)

Baseline disease characteristics:

- Subjects positive to at least one diabetes-related autoantibody: 1, >1-<=3 and >3
- Baseline HbA1c categories: ≤6.5%, >6.5%
- Baseline C-peptide AUC: <0.66 pmol/mL or ≥0.66 pmol/mL
- Baseline insulin usage by quantiles
- Number of days since diagnosis of T1D: < 60 days or ≥ 60 days

In addition, subgroup analyses defined by Human Leukocyte Antigen (HLA)-DR3 presence/absence, and HLA-DR4 presence/absence will be explored for selected endpoints (See Section 5.5.2).

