4.1. Inclusion Criteria

4.1.1. Inclusion Criteria Applicable to All Subjects

Each potential subject must satisfy all of the following criteria to be enrolled in the study:

1. Male or female 6 through 21 years of age who are diagnosed with T1D within 100 days of randomization per the ADA standard T1D criteria.⁷⁰
2. Be positive for at least 1 of the following diabetes-related autoantibodies obtained at study screening:
 - Glutamic acid decarboxylase (GAD-65)
 - IA-2
 - ZnT8
 - ICA; or
 - Insulin (if obtained within 10 days of the onset of exogenous insulin therapy)
3. Have a peak stimulated C-peptide level ≥ 0.2 pmol/mL following a 4-hour MMTT obtained at study screening.
4. Be medically stable on the basis of physical examination, medical history, and vital signs performed at screening. If there are abnormalities, they must be consistent with the underlying illness in the study population.
5. Females of childbearing potential must have a negative serum (β -human chorionic gonadotropin [β -hCG]) test at screening and a negative urine pregnancy test at the Week 0 visit.
6. Criterion modified per Amendment 3 – open-label extension period
 - 6.1. Females must be either:
 - Not of childbearing potential: premenarchal; permanently sterilized (eg, tubal occlusion, hysterectomy, bilateral salpingectomy); or otherwise be incapable of pregnancy,

OR

- Of childbearing potential, and if sexually active, practicing through Week 104 and open-label extension period of the study be practicing a highly effective method of birth control consistent with local regulations regarding the use of birth control methods for subjects participating in clinical studies: eg, established use of oral, injected or implanted hormonal methods of contraception; placement of an intrauterine device (IUD) or intrauterine system (IUS); barrier methods: condom with spermicidal foam/gel/film/cream/suppository or occlusive cap (diaphragm or cervical/vault caps) with spermicidal foam/gel/film/cream/suppository; male partner sterilization (the vasectomized partner should be the sole partner for that subject); true abstinence (when this is in line with the preferred and usual lifestyle of the subject).
- Females of childbearing potential must agree not to donate eggs (ova, oocytes) for the purposes of assisted reproduction through Week 104 and open-label extension period.

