4.1. Demographics and Baseline Characteristics

Demographic (age, race, sex, height, weight and BMI) and baseline characteristic variables will be summarized by randomized treatment groups and overall (all treatments pooled together) for

all subjects randomized. Descriptive statistics (N, mean, SD, median, and range) will be provided for continuous variables at baseline as well as the number and percentage of subjects for categorical variables.

Baseline disease characteristics to be summarized will include but not limited to: number of days since diagnosis of T1D, fasting blood glucose prior MMTT, 4-h peak C-peptide, 4-h C-peptide AUC, 2-h C-peptide AUC, HbA1C, insulin use unit per day, and subjects positive to at least one diabetes-related autoantibody.

In addition, the number and percentage of subjects in the following categories will be summarized by treatment group:

- Age :<12 years, 12-18 years, >18 years
- Weight: <45 kg, ≥45 kg
- Number of positive diabetes-related autoantibodies: 1, >1-≤3 and >3
- Type of positive diabetes-related autoantibody: GAD-65, IA-2, ZnT8, ICA, and insulin
- Baseline HbA_{1c}: ≤6.5%, >6.5%
- Number of days since diagnosis of T1D: < 60, ≥60

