5.3.2.1. Subgroup Analysis for the Primary Endpoint

The treatment difference of the primary endpoint by each subgroup factor listed in Section 2.3 will be explored and presented through forest plots. Subgroup analysis will not be performed on the sensitivity analyses described below.

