7. CLINICAL PHARMACOLOGY

7.1. Pharmacokinetics

Pharmacokinetics (PK) samples for measuring serum golimumab concentrations will be collected from all subjects at the specified visits as shown in the schedule of events of the protocol. All PK evaluations will be based on the subjects who receive at least 1 injection of golimumab (PKE analysis set). No imputation for missing concentration data will be performed.

The data analysis of serum golimumab concentrations includes the following:

- Summary of serum golimumab concentrations at each visit by treatment group
- Summary of serum golimumab concentrations at each visit by age group (≥ 6 to < 12 Years, ≥ 12 to < 21 Years)
- Summary of serum golimumab concentrations by treatment group and by body weight quartiles
- Summary of serum golimumab concentrations by treatment group and by body weight category (< 45 kg, ≥ 45 kg)
- Proportion of subjects without detectable serum golimumab concentration at each visit by treatment group
- Median serum golimumab concentrations plotted over time by treatment group

In addition, the relationship between serum golimumab concentrations, and antibody to golimumab status, safety and efficacy may be explored using graphical displays.

For summary statistics of serum golimumab concentrations, concentration values below the lower limit of quantification will be treated as zero. Once a subject meets one of the following dosing deviation criteria, the subject's data will be excluded from the by-visit data analyses from that point onwards.

Dosing deviation criteria:

- Discontinue SC study agent administration

- Skipped an SC administration
- Received an incomplete/incorrect SC dose
- Received an incorrect SC study agent
- Received and additional SC dose

In addition, if a subject has an administration more than 7 days earlier or later than the scheduled dosing date, the concentration data collected between such a dosing visit and the subsequent dosing visit will be excluded from the by-visit data analyses. For the Week 26 visit, if the PK sampling time deviates more than 3 days earlier or later than the scheduled date, the PK concentration at this visit will be excluded from the by-visit data analyses. Additional exclusions for incongruous PK data to be implemented based on Janssen SOP-07948v2.

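### With age in whole years, the SAP 2.4 age subgroups overlap at 18 and disagree with SAP 4.1, and the SAP 7.1 PK age groups omit eligible 21-year-olds

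*SAP*

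**What the plan says.** Four places bear on this.

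- **Eligibility.** Protocol 4.1.1, criterion 1, admits "Male or female 6 through 21 years of age", so 21 is included. SAP 2.2.1 likewise matches the external placebo subjects to ages between 6 and 21.
- **Efficacy subgroups.** SAP 2.4 gives "Baseline Age (<12, 12-18, ≥18"). It performs a subgroup analysis only where each treatment group has at least 5 subjects in the subset.
- **Baseline table.** SAP 4.1 gives "Age :<12 years, 12-18 years, >18 years".
- **PK summary.** SAP 7.1 plans a "Summary of serum golimumab concentrations at each visit by age group (≥ 6 to < 12 Years, ≥ 12 to < 21 Years").

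The SAP 2.4 bands are used in SAP 5.3.2.1: "The treatment difference of the primary endpoint by each subgroup factor listed in Section 2.3 will be explored and presented through forest plots". SAP 5.4.2.3 does the same for the major secondary endpoints. Both cite Section 2.3, which defines baseline measurements; the subgroup list is in Section 2.4. So the cross-reference offers no further definition of the age bands.

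**The concern.** Subgroup bands should place each eligible subject in exactly one group. Two of the three age lists in the SAP do not.

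If SAP 2.4 is programmed literally, 18-year-olds contribute to two rows of the same forest plot, and the two estimates share data. If a programmer instead resolves the overlap, the SAP does not say which way. The answer could also affect whether the oldest row appears, because of the minimum of 5 per arm. A decision of that kind should not be left until after unblinding.

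In the PK summary the fault is an omission: golimumab subjects aged 21 are treated and sampled but drop out of the age breakdown.

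**Working it through.** No figure in the plan has to be reproduced for this point. The check is to assign each whole-year age from 6 to 21 to the bands as written and count the bands it meets. A valid partition gives one every time.

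| List | Ages 6–17 | Age 18 | Ages 19–20 | Age 21 |
|---|---|---|---|---|
| SAP 2.4: <12, 12-18, ≥18 | 1 | **2** | 1 | 1 |
| SAP 4.1: <12, 12-18, >18 | 1 | 1 | 1 | 1 |
| SAP 7.1: ≥6 to <12, ≥12 to <21 | 1 | 1 | 1 | **0** |

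The boundaries at 6 and 12 are sound. The faults are the cut at 18 in SAP 2.4 and the upper limit in SAP 7.1.

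**Number of subjects affected.** The planned sizes are 81 in total, 54 on golimumab and 27 on placebo (protocol 11.2, SAP 1.4). The age distribution is not given, so I assume a share p of subjects at each single year of age and show a range.

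- In two efficacy subgroups: 81 × p. At p = 2%, 81 × 0.02 = 1.6; at p = 10%, 81 × 0.10 = 8.1. About 2 to 8 subjects.
- Missing from PK by age: 54 × p. At p = 2%, 54 × 0.02 = 1.1; at p = 10%, 54 × 0.10 = 5.4. About 1 to 5 subjects.
- An even spread over the 16 years (p = 1/16 = 6.25%) lies inside that range: 81/16 = 5.1 and 54/16 = 3.4.

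**The minimum of 5 per arm.** Placebo is the smaller arm. The expected placebo count in the oldest band is 27 × 4p if 18-year-olds are in it (ages 18 to 21) and 27 × 3p if not (ages 19 to 21).

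| p | With 18-year-olds | Without |
|---|---|---|
| 2% | 2.2 | 1.6 |
| 6.25% (even spread) | 6.8 | 5.1 |
| 10% | 10.8 | 8.1 |

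The expected count reaches 5 at p = 5/108 = 4.6% with the 18-year-olds and at p = 5/81 = 6.2% without them. Between those shares, the placement of the 18-year-olds decides on which side of 5 the expected count falls. Actual counts vary around expectation: under the even spread, the chance of fewer than 5 placebo subjects is about 16% with them, from Binomial(27, 4/16), and about 41% without, from Binomial(27, 3/16).

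**Decimal age.** The SAP does not say in these sections whether age is in whole years. With decimal age, the SAP 2.4 overlap and the mismatch with SAP 4.1 shrink to a subject aged exactly 18.0, so almost nobody. The PK gap stays, because anyone past the 21st birthday is outside the upper band.

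**After correction.** The bands <12, 12 to <18, ≥18 and the bands <12, 12-18, >18 each place every age from 6 to 21 once. So do PK bands of 6 to <12 and 12 through 21.

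**The case against.** The best reply is that this is a wording slip with little reach, and much of that stands. The primary MMRM in SAP 5.3.2 carries age as a continuous covariate, so the bands do not enter it. The subgroup results are described as exploratory. Subjects aged 21 remain in the overall PK summary and in the summaries by body weight, and any population PK analysis under SAP 7.1 may examine age as a covariate. Protocol section 1 says type 1 diabetes presents most often in childhood and adolescence, which suggests that the shares at 18 and 21 may lie towards the low end of the range.

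It can also be said that 12-18 was meant as 12 to under 18. That is possible, but the SAP does not say so, and SAP 4.1 pairs the same label with a top band of over 18, where an 18-year-old can only belong to 12-18. The two readings have different effects. If 12-18 includes 18, SAP 2.4 puts the subject in two groups, one of which agrees with the baseline table. If it excludes 18, nobody is counted twice, but the forest plot and the baseline table place the subject differently. Either way the sections need aligning.

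A reader might infer more from the protocol's introduction, which calls age the most important factor in the rate of C-peptide decline, and conclude that the cut at 18 is critical. The documents do not support this: the contrast reported there is 21 and younger against 22 and older, which lies outside the enrolled range and says nothing about a division at 18.

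**Conclusion.** With age in whole years, SAP 2.4 is not a valid partition at 18 and differs from SAP 4.1, and SAP 7.1 has no group for eligible 21-year-olds. Nothing elsewhere in the documents resolves either point.

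The size is modest and uncertain: about 2 to 8 of 81 subjects in two efficacy subgroups and about 1 to 5 of 54 golimumab subjects missing from the PK-by-age summary, on an assumed 2% to 10% of subjects at each single year. With decimal age only the PK gap matters. Whether the oldest forest-plot row meets the minimum of 5 per arm may turn on where the 18-year-olds go, but this depends on an age distribution that the documents do not give.

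A reader might go further and take the age banding as wrong throughout, or as a threat to the primary result. Neither follows: the lower boundaries are correct, and no hypothesis test, alpha level or sample size depends on these bands.

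**What to change.** Before the Week 52 database lock, make these edits to the SAP:

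1. Use one non-overlapping set of age bands in SAP 2.4 and 4.1. Either change ≥18 to >18 in 2.4, which matches 4.1 as it stands, or use <12, 12 to <18 and ≥18 in both. The first is the smaller edit. The second follows the division at 18 that the protocol uses for its HbA1c targets and blood-volume limits. Both are sound.
2. In SAP 7.1, define the upper PK group as ≥12 through 21 inclusive.
3. State that age is in completed years, so that the labels 18 and 21 have one meaning.

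The Section 2.3 references in SAP 5.3.2.1 and 5.4.2.3 can be corrected to Section 2.4 at the same time.

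The cost is a few words of text. Data collection, sample size and the primary analysis do not change.
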